#### **9.4.3.2. Laboratory Results**

Descriptive statistics (N, mean, SD, median, Q1, Q3, minimum, and maximum) will be provided for each continuous laboratory test as follows:

- Baseline values
- Values at each postbaseline analysis window (to be defined in the SAP)
- Change from baseline at each postbaseline analysis window

The minimum, maximum, and last postbaseline value / change from baseline will also be summarized. Missing data will not be imputed.

Laboratory tests will be descriptively analyzed by grade and analysis window using counts and percentages. The maximum and last postbaseline grade for each participant will also be summarized. Denominators will be the number of participants with a graded (or normal) test during the window. Laboratory tests with criteria for both increased and decreased levels will be analyzed for each direction (i.e., increased and decreased). This analysis will be generated twice to count (1) treatment-emergent increases in laboratory grades (i.e., only those above the baseline grade) and (2) any grade regardless of baseline.

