Aspartate Aminotransferase (AST)	>ULN - 3.0 x ULN	>3.0 - 5.0 x ULN	>5.0 - 20.0 x ULN	>20.0 x ULN
Alanine Aminotransferase (ALT)	>ULN - 3.0 x ULN	>3.0 - 5.0 x ULN	>5.0 - 20.0 x ULN	>20.0 x ULN
Total Bilirubin	>ULN - 1.5 x ULN	>1.5 - 3.0 x ULN	>3.0 - 10.0 x ULN	>10.0 x ULN
Creatinine	>ULN - 1.5 x ULN	>1.5 - 3.0 x ULN	>3.0 - 6.0 x ULN	>6.0 x ULN
Creatinine Clearance, Estimated	<LLN - 60 ml/min	<60 - 30 ml/min	<30 - 15 ml/min	<15 ml/min

NA = Not applicable, ULN = Upper limit of normal, LLN = Lower limit of normal.

Grade 0 : Any result not graded 1, 2, 3, 4 or Unknown.

Grade Unknown : Missing result or missing upper limit of normal for parameters requiring ULN for grading.

(Notes for programmer:

- LLN for creatinine clearance is fixed 90 mL/min
- Calculation of creatinine clearance (CC) (Cockcroft-Gault):

$$(140 - \text{age (years)})$$

$$CC \text{ (ml/min)} = \frac{140 - \text{age (years)}}{0.8143 \times \text{serum creatinine (}\mu\text{mol/L)}} \times \text{baseline weight (kg)} \times (0.85 \text{ if female})$$

)

Table 14: Distribution of laboratory grade by parameter and visit - Safety Set

Parameter: <Hemoglobin> <Platelets> <Activated partial thromboplastin time (aPTT)> <Prothrombin International Normalized Ratio (INR)> <Aspartate aminotransferase (AST)> <Alanine aminotransferase (ALT)> <Total bilirubin> <Creatinine> <Creatinine Clearance, Estimated >

Scheduled Visit Grades (a)	DSTAT 0.25 N=xxx	Cohort 1 PBO N=xxx	DSTAT 0.325 N=xxx	Cohort 2 PBO N=xxx
Baseline				
Grade 0	xx (xx.x)	xx (xx.x)	xx (xx.x)	xx (xx.x)
Grade 1	xx (xx.x)	xx (xx.x)	xx (xx.x)	xx (xx.x)
Grade 2	xx (xx.x)	xx (xx.x)	xx (xx.x)	xx (xx.x)
Grade 3	xx (xx.x)	xx (xx.x)	xx (xx.x)	xx (xx.x)
Grade 4	xx (xx.x)	xx (xx.x)	xx (xx.x)	xx (xx.x)
Unknown	xx (xx.x)	xx (xx.x)	xx (xx.x)	xx (xx.x)
Maximum Post-baseline Grade				
Grade 0	xx (xx.x)	xx (xx.x)	xx (xx.x)	xx (xx.x)
Grade 1	xx (xx.x)	xx (xx.x)	xx (xx.x)	xx (xx.x)
Grade 2	xx (xx.x)	xx (xx.x)	xx (xx.x)	xx (xx.x)
Grade 3	xx (xx.x)	xx (xx.x)	xx (xx.x)	xx (xx.x)
Grade 4	xx (xx.x)	xx (xx.x)	xx (xx.x)	xx (xx.x)
Unknown	xx (xx.x)	xx (xx.x)	xx (xx.x)	xx (xx.x)

N = Number of subjects in a specific group; n = Number of subjects with data available; Percentages are based on N; (a) CTCAE v5.0 grades using absolute thresholds without accounting for baseline.

Baseline value is defined as the last non-missing measurement prior to, or on the date/time of the first administration of study treatment.

NA = not applicable

Page X of Y

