(Notes for programmer:

- CTCAE Grades: Unknown: missing result (or missing upper limit of normal for parameters requiring ULN for grading). Grade 0: any result not graded 1, 2, 3, 4 or Unknown.
- display only for visit Baseline and Maximum Grade per subject and all 6 categories (Grade 0 - Grade 4 and Unknown), if applicable.
- generate a post-baseline Maximum Grade per subject (incl. unscheduled measurements)
- for the generation of Maximum Grade use the following order: Unknown - Grade 0 - Grade 1, ..., Grade 4)
- Calculation of creatinine clearance (CC) (Cockcroft-Gault):
(140 - age (years))

CC (ml/min) = ----- * baseline weight (kg) * (0.85 if female)
0.8143 * serum creatinine (μmol/L)

)

Table 15: Listing of laboratory results - Safety Set

Subject Age/Sex/Race	Treatment Group	Parameter	Date/Time	Visit	Value \$	Unit	Lower Limit	Upper Limit	Grade (a)	
999-999 70/F/W	DSTAT 0.25	Hemoglobin	Ddmmmyy/mm:hh	Screening	99999 H	NCS	Unit	LLL	UUU	1
			Ddmmmyy/mm:hh	Baseline	99999 L	CS	Unit	LLL	UUU	4

(a) CTCAE v5.0 grades using absolute thresholds without accounting for baseline. Grade=0 and Grade=Unknown are not displayed.
\$: H = Above upper limit of normal; L = Below lower limit of normal, NCS = Not clinically significant, CS= Clinically significant.
Visit "Early Tx DC (TXDC)" denotes Early Treatment Discontinuation Visit.

(Notes for programmer:

- Sorted by subject number, Parameter, date and time
- The following parameter will be displayed: Hemoglobin, platelets, activated partial thromboplastin time (aPTT), prothrombin time (PT), prothrombin international normal ratio (INR), d-dimer, Anti-Xa, aspartate aminotransferase (AST), alanine aminotransferase (ALT), total bilirubin, creatinine, Creatinine Clearance, Estimated.
- LLN for creatinine clearance is fixed 90 mL/min
- CTCAE Grades: reference Table 13.)

Table 16: Shift-table of laboratory results - Safety Set

Parameter: <Hemoglobin> <Platelets> <Activated partial thromboplastin time (aPTT)> <prothrombin time (PT)> <Prothrombin International Normalized Ratio (INR)> <d-dimer> <Anti-Xa> <Aspartate aminotransferase (AST)> <Alanine aminotransferase (ALT)> <Total bilirubin> <Creatinine> <Creatinine Clearance, Estimated>

DSTAT 0.25 N=xxx				Cohort 1 PBO N=xxx				Baseline (D1)				DSTAT 0.325 N=xxx				Cohort 2 PBO N=xxx																										
<LLN			Normal	>ULN			<LLN			Normal	>ULN			<LLN			Normal	>ULN			<LLN			Normal	>ULN																	
Post-Baseline																																										

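### SAP Table 14 departs from protocol 9.4.3.2 on graded laboratory results (no treatment-emergent version, by-window grades or last grade; percentages on all N) and does not declare it

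*SAP*

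**What the plan says.** Protocol 9.4.3.2 sets four requirements for graded laboratory tests and limits none of them to a phase or cohort.

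- By window: "Laboratory tests will be descriptively analyzed by grade and analysis window using counts and percentages".
- Maximum and last: "The maximum and last postbaseline grade for each participant will also be summarized".
- Denominator: "Denominators will be the number of participants with a graded (or normal) test during the window".
- Two versions: "This analysis will be generated twice to count (1) treatment-emergent increases in laboratory grades (i.e., only those above the baseline grade"), and a second count of any grade regardless of baseline.

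SAP 5.1, Table 14 is titled "Distribution of laboratory grade by parameter and visit - Safety Set". Its programmer note restricts it: "display only for visit Baseline and Maximum Grade per subject and all 6 categories". Its footnote reads "Percentages are based on N; (a) CTCAE v5.0 grades using absolute thresholds without accounting for baseline", where N is the number of subjects in the group and Unknown is one of the six categories.

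SAP section 1 says that the document is based on protocol Amendment 3. The SAP contains no statement of departures from it.

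**The concern.** The distribution of graded laboratory results is a named safety endpoint in protocol section 3. The table that should report it leaves out the version that separates new or worsened abnormalities from those present at entry. It also leaves out the displays that would show whether an abnormality resolved. Its title promises results by visit, but its note shows only two columns of time.

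Two tests show what is at stake.

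- **Hemoglobin.** Protocol 4.3 calls serious bleeding the primary toxicity. No numeric hemoglobin limit applies at entry; there is only investigator judgment under exclusion 23. One Grade 3 (<8.0 g/dL in SAP Table 13) at baseline and one Grade 3 maximum could be the same participant or a new case.
- **ALT.** Protocol 4.3 describes a rise that returns to baseline after treatment stops. A maximum-only table cannot separate a Grade 2 that resolved from one that persisted.

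SAP section 2 describes this part of the package as equivalent to the output given to the DMC for Cohort 2, so the same layout also serves a safety review.

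**Working it through.** The plan states no figure to reproduce. The check compares the two texts, searches for other outputs that fill the gap, and then sizes the effect on assumed data.

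**1. Requirement against display**

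| Protocol 9.4.3.2 | SAP Table 14 |
|---|---|
| Treatment-emergent and any-grade versions | Any-grade only; baseline not accounted for |
| Grades by analysis window | Baseline and Maximum only |
| Maximum and last post-baseline grade | Maximum only |
| Denominator: participants with a graded or normal test | All N, with Unknown as a row inside N |

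**2. Other SAP outputs**

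- Table 15 is a listing of values, limits and grades.
- Table 16 shifts only between <LLN, Normal and >ULN.
- Figure 3 plots values, not grades.
- Section 5.2 has no graded laboratory table.

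No summary table supplies the missing items. Protocol Table 1 schedules hematology and chemistry on 6 post-baseline days (2, 4, 6, 8, 14, 28), against one maximum shown.

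**3. Can the number who worsened be read from Table 14?**

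Group size: N=8, the planned Cohort 2 dociparstat group (protocol 4.1). The grades below are assumed, because the documents give no expected counts. Table 16 is held fixed: 3 participants stay Normal and 5 stay out of range.

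Hemoglobin: baseline {0,0,0,1,1,1,2,3}, maximum {0,0,0,1,1,2,2,3}. These pairings for the 5 out-of-range participants all give the same Table 14 and Table 16 entries:

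| Baseline to maximum | Worsened | Maximum better than baseline | New Grade 3 |
|---|---|---|---|
| 1→1, 1→1, 1→2, 2→2, 3→3 | 1 (12.5%) | 0 | 0 |
| 1→1, 1→2, 1→2, 2→1, 3→3 | 2 (25.0%) | 1 | 0 |
| 1→1, 1→1, 1→2, 2→3, 3→2 | 2 (25.0%) | 1 | 1 |
| 1→1, 1→2, 1→2, 2→3, 3→1 | 3 (37.5%) | 1 | 1 |

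The grades sum to 8 at baseline and 9 at maximum. If nobody's maximum is below baseline, the total rise is 9 − 8 = 1, so exactly 1 participant worsened and none is newly Grade 3. Every other row needs someone whose worst post-baseline grade, unscheduled tests included, is better than baseline.

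ALT, Grades 0-2 only: baseline {0,0,0,1,1,1,2,2}, maximum {0,0,0,1,1,2,2,2}. Again 1, 2 or 3 worsened, with no new Grade 3. The sums are 7 and 8, so exactly 1 if nobody improves.

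**4. Denominator**

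Table 14 gives x/N; the protocol gives x/(N − u), where u is the number with no gradable result. With x=1:

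| N | u=0 | u=1 | u=2 |
|---|---|---|---|
| 4 | 25.0% both | 25.0% vs 33.3% | 25.0% vs 50.0% |
| 6 | 16.7% both | 16.7% vs 20.0% | 16.7% vs 25.0% |
| 8 | 12.5% both | 12.5% vs 14.3% | 12.5% vs 16.7% |

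x and u are assumptions. There is no difference when u=0.

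**5. Where entry limits remove the ambiguity (protocol 5.2)**

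- ALT/AST >5x ULN is excluded, so a post-baseline Grade 3 or higher is normally new.
- Creatinine clearance <30 mL/min is excluded, so here too Grade 3 or higher is normally new.
- aPTT >42 seconds is excluded. With the SAP's 25-35 second range for Figure 3, Grade 2 starts above 1.5 × 35 = 52.5 seconds, so Grade 2 or higher is normally new.
- Platelets <80,000/mm³ are excluded, so a count below 75,000/mm³ is normally new.
- Hemoglobin, INR and bilirubin have no numeric entry limit.

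**6. Recovery by hand**

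The ceiling is 9 parameters × 24 participants (6+6+8+4) = 216 baseline-to-maximum comparisons from Table 15.

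**The case against.** The strongest reply is that this is a reduced package for about 24 participants, that protocol 9.4 calls for descriptive presentation of Cohorts 1 and 2, and that a Phase 2 SAP is due before the Cohort 3 analysis and could carry the full set. That limits the weight of the point. It does not remove it: 9.4.3.2 is itself descriptive and exempts no cohort, and this SAP neither defers the missing outputs nor calls itself reduced.

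Other parts of the defence stand.

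- **Table 15.** A reader might infer from "Grade=0 and Grade=Unknown are not displayed" that worsening cannot be rebuilt from the listing. It can. Values and limits are printed, so a missing value or missing upper limit identifies an Unknown. Series with no printed post-baseline grade need no check for worsening, so 216 is a ceiling.
- **Bleeding.** A reader might infer that bleeding harm could go unseen. The documents do not support that. Bleeding AEs are AEs of special interest (protocol 8.4.6) and are listed individually in SAP Table 12. Clinically significant laboratory changes are recorded as AEs (protocol 8.3.4) and can appear in Tables 8 and 9.
- **Range of 1 to 3.** A reader might take these as equally plausible. They are not: 2 or 3 worsened, and any new Grade 3, require a participant whose worst post-baseline grade beats baseline.
- **Denominator.** This is the weakest element. Unknown has its own row and ranks lowest, so count/(N − Unknown) restores the protocol percentage, provided that subjects with no sample are counted as Unknown. The protocol rule also speaks of tests within a window, and Baseline and Maximum are not clearly windows.

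**Conclusion.** The departure is real and undeclared. Table 14 omits the treatment-emergent version, by-window grades and last post-baseline grade that the protocol requires, and uses a different denominator. The missing treatment-emergent version matters most.

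The size is modest. No test, power or error rate is affected, and nothing in the documents shows that a dosing recommendation would change. On assumed data with N=8, the tables fit 1, 2 or 3 participants who worsened, falling to exactly 1 if nobody's worst post-baseline grade improves on baseline. The ambiguity lies mainly in Grades 1-2 and in hemoglobin, INR and bilirubin. It should be corrected because it concerns a named safety endpoint and a firm protocol commitment, not because the safety data would otherwise be lost.

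**What to change.** 1. Add to Table 14 a treatment-emergent panel: maximum post-baseline grade above baseline grade. State how an Unknown baseline grade is counted.
2. Add a last post-baseline grade panel.
3. Base percentages on participants with a graded or normal test, and keep the Unknown count visible.
4. For by-window grades, choose one of two courses. Either define laboratory analysis windows, which protocol 9.4.3.2 leaves to the SAP and this SAP does not define, and add the grades. Or state that the reduced Cohort 1/2 display is a deliberate deviation from 9.4.3.2.
5. Align the title of Table 14 with what it shows.

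The cost is a footnote edit and a few programmed panels, plus window definitions if by-window grades are added. No new data are needed, since results are already graded for Tables 14 and 15.

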#### **6.6.2. Permitted Therapies**

The following medications are permitted during the study:

- Medications for acute (e.g., pain, bacterial infection) or chronic (e.g., hypertension, diabetes) medical conditions, unless otherwise prohibited.
- Prophylaxis for venous thromboembolism using SC unfractionated heparin or enoxaparin with appropriate monitoring of coagulation status. See [Appendix 8](#) for guidelines.
- Remdesivir, per available data sheets/guidance on dosing and toxicity management.
- Convalescent plasma.

For participant's whose condition declines to a 2 on the NIAID ordinal scale (i.e., requires invasive mechanical ventilation or extracorporeal membrane oxygenation), otherwise prohibited treatments may be initiated at the investigator's discretion. In this situation, please contact the medical monitor since discontinuation of study intervention may be warranted if use of an otherwise prohibited treatment (e.g., therapeutic anticoagulant doses) could affect the participant's safety if study intervention were to be continued.

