## 7.2. Discontinuation of Study Intervention

In some instances, it may be necessary for a participant to permanently discontinue study intervention before completing the protocol-specified treatment period. Reasons for permanent discontinuation of study intervention may include the following:

- Criteria for restarting study intervention after interruption were not met.
- ALT  $\geq 3$ x ULN (and  $>2$ x baseline value) plus bilirubin  $\geq 2$ x ULN.
- Thrombocytopenia defined as a platelet count of  $<30,000/\text{mm}^3$ .
- Hemorrhagic AE of Grade 3 or higher (graded according to the National Cancer Institute-Common Terminology Criteria for Adverse Events [NCI-CTCAE]).
- Other treatment-related AE of unacceptable severity.
- Condition has improved and participant is eligible for hospital discharge.
- Participant requests to discontinue study intervention.
- Investigator initiates treatment with a therapeutic anticoagulant dose, a thrombolytic agent, or otherwise prohibited therapy that may affect the participant's safety if study intervention were to be continued.
- Investigator determines discontinuation is in the best interests of the participant for safety, behavioral, compliance, or administrative reasons.

Participants who discontinue study intervention early will complete the early discontinuation assessments (refer to the Schedule of Assessments) and will continue to be followed-up through Day 28.

Note: For participants who are discharged from the hospital prior to Day 8, the next visit will be Day 14.

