### 8.3.4. Clinical Laboratory Assessments

All required laboratory assessments must be conducted in accordance with this protocol and the laboratory manual. The timing and frequency of laboratory assessments are specified in the Schedule of Assessments (Table 1).

- The laboratory tests (clinical chemistry, hematology, and coagulation) listed in Table 4 will be performed by the study centers' usual local laboratory, unless otherwise specified.
- All laboratory reports will be filed with the source documents.
- Site personnel must enter results into the eCRF for the specified laboratory parameters (with units and relevant reference ranges) at each specified time point.
- The investigator must document their review of each laboratory report. Clinically-relevant abnormal laboratory findings at screening and before the first dose of study intervention will be recorded as medical history.

- Clinically significant abnormal changes occurring within 28 days after first dose of study intervention will be recorded in the eCRF as an AE(s).
  - These laboratory tests will be repeated (and recorded in the eCRF) until the values return to normal or baseline or are no longer considered clinically significant by the investigator.
  - If such values do not return to normal/baseline within a period of time judged reasonable by the investigator, the etiology should be identified.
  - The investigator may consult with the medical monitor for any questions.

Laboratory tests may be performed at additional times during the study as part of standard care, as determined necessary by the investigator, or as required by local regulations. Any laboratory test(s) performed in response to an AE must be recorded in the participants' eCRF (as an unscheduled visit if not at a protocol-specified time point).

Refer to Section 5.2 for laboratory-related participant exclusion criteria and Section 7 for laboratory-related criteria for interruption and discontinuation of study intervention.

Study center staff must enter results of all local/institutional laboratory results into the eCRF. Instructions for collection, handling, and shipment of samples for central analysis is included in the laboratory manual.

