2. INTRODUCTION

Cohort 1 contains 6 participants randomized to dociparstat, 6 randomized to placebo. Dociparstat will be dosed as 4 mg/kg IV bolus followed by continuous infusion of 0.25 mg/kg/hr.

Cohort 2 includes 6 participants randomized to dociparstat, 6 randomized to placebo. Dociparstat will be dosed as 4 mg/kg IV bolus followed by continuous infusion of 0.325 mg/kg/hr (dose to be confirmed after review of data from Cohort 1).

Based on Protocol Amendment 3, dated 06 November 2020, the randomization ratio (dociparstat: placebo) changed from 1:1 in Cohort 1 to 2:1 in the following cohorts.

Both Cohorts 1 and 2 may be unblinded to the entire team following cleaning and database lock of Cohort 1/2 data. The full randomization code will remain blinded as is; in this event, only the Cohort 1/2 assignments will be unblinded.

The first part of the analysis defined in this document will be equivalent to the statistical output delivered to the DMC-members for the 2nd Cohort (see Section 5.1), however with all data collected until End of Study (EOS).

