Minimum, n (%)																																										
<LLN																																										
Normal																																										
>ULN																																										
Post-Baseline																																										
Maximum, n (%)																																										
<LLN																																										
Normal																																										
>ULN																																										

N = Number of subjects in a specific group; n = Number of subjects with data available; Percentages are based on N;

Normal: Within normal range, LLN: Lower limit of normal, ULN: Upper limit of normal.

Only subjects with baseline and at least one post-baseline value are considered.

Baseline value is defined as the last non-missing measurement prior to, or on the date/time of the first administration of study treatment. NA = not applicable.

Page X of Y

(Notes for programmer:

- generate a post-baseline Maximum Value and post-baseline Minimum Value per subject (incl. unscheduled measurements
- LLN for creatinine clearance is fixed 90 mL/min
- if ULN (eg CC) available, please display n/a
-)

Figure 3: Selected laboratory parameters over time (Box-Whisker-Plot) - Safety Set

Box-Whisker-Plots: by <Parameter> (<unit>), Cohort X, Reference Ranges xxx - yyyy <unit>

y-axis:

range: depending on data
label: Value

x-axis:

range: Visits : Screening, D1 to D28 (depending on data) visit. Incl Early Tx DC at the end of the x-axis.

label: Visit

Box-Whisker Plots:

different styles/colors for the treatment-groups

Plots shifted to not overlap

Default SAS Box-Whisker-Plots - Min, 25%, Median, 75%, Max. Whiskers as 1.5 IQR. Mean included.

Footnotes to be used for the Box-Whisker-Plots :

Visit "Early Tx DC (TXDC)" denotes Early Treatment Discontinuation Visit. Reference Ranges do not necessarily present "values of concern" in this population but will give some context to the results relative to a normal population.

(Notes for programmer:

- replace <Parameter> <unit>, in label by actual parameter and unit used
- Adapt Visits as relevant for the different parameters. Not all parameters are reported for all visits, only scheduled visits to be included in the Figure

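### Tables 14 and 16 have no on-treatment window, so an aPTT or INR value taken under therapeutic anticoagulation after study drug has stopped can set a participant's only displayed post-baseline grade or shift

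*SAP*

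**What the plan says.** SAP section 5.1 sets the rule in the programmer notes.

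- Table 14 (laboratory grades, including aPTT and INR): "generate a post-baseline Maximum Grade per subject (incl. unscheduled measurements". The same notes say "display only for visit Baseline and Maximum Grade per subject", so the table has no by-visit or on-treatment row.
- Table 16 (shifts between below, within and above the normal range, covering aPTT, PT, INR and anti-Xa among others): "generate a post-baseline Maximum Value and post-baseline Minimum Value per subject (incl. unscheduled measurements".
- SAP section 2 says that this part of the package matches the DMC output for the second cohort, "however with all data collected until End of Study (EOS".

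The protocol supplies the rest.

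- The Schedule of Activities (Table 1) has aPTT and PT/INR at screening, on Days 1 to 7 and at early therapy discontinuation. None is scheduled on Day 8, 14 or 28.
- Section 7.2 lists among the reasons for permanent discontinuation: "Investigator initiates treatment with a therapeutic anticoagulant dose, a thrombolytic agent, or otherwise prohibited therapy". These participants stay in follow-up to Day 28.
- Section 6.6.2 says that after decline to NIAID score 2 "otherwise prohibited treatments may be initiated at the investigator's discretion", and gives therapeutic anticoagulant doses as its example.
- Section 8.3.4: "Study center staff must enter results of all local/institutional laboratory results into the eCRF".
- Section 9.4.3.2 calls for a maximum, but not on its own: "The maximum and last postbaseline grade for each participant will also be summarized". It also asks for summaries by analysis window and for treatment-emergent grades.

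**The concern.** Prolonged aPTT is one of the risks of particular interest in protocol section 2.3.1, and Tables 14 and 16 are the package's only grade and shift summaries for it. A participant who stops study drug and then receives heparin at therapeutic intensity may have aPTT drawn for clinical monitoring. If that result is entered, it competes with the on-infusion values for the maximum, and nothing in the table shows which of them won. The reader then sees an abnormal grade under the randomised arm and may attribute it to study drug, or see one under placebo and discount a real difference. In arms this small, one participant is enough to change the impression.

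**Working it through.** The documents give no figure for how often this happens, so there is no plan figure to reproduce. The check traces the route and then sizes it under stated assumptions.

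**1. Is the route open?** After a completed infusion, any later aPTT or INR must be an unscheduled draw, and the rule includes unscheduled draws. After early discontinuation, the scheduled draw at that visit may itself follow the start of an anticoagulant. The data run to end of study and no cut-off applies. The route is open.

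**2. Weight of one participant.** Arm sizes are 6 and 6 in Cohort 1. Cohort 2 is 8 and 4 in protocol section 4.1 but 6 and 6 in SAP section 2; these must be reconciled, and the point holds for either. One participant is 100/8 = 12.5, 100/6 = 16.7 or 100/4 = 25 percentage points.

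**3. Chance of at least one affected participant in an arm.** Let q be the probability that a post-drug value sets a participant's abnormal grade (an assumption). The chance is 1 − (1 − q)^n.

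| q | n = 4 | n = 6 | n = 8 |
|---|---|---|---|
| 5% | 18.5% | 26.5% | 33.7% |
| 20% | 59.0% | 73.8% | 83.2% |

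The 20% is the protocol's planning rate for ventilation or death on placebo, used only as an upper-end stand-in.

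**4. Effect on the drug-placebo contrast.** Let p be the on-infusion probability of the abnormal grade. If the two sources are independent, the table shows 1 − (1 − p)(1 − q). Assume p = 0.30 on drug and 0.05 on placebo, a true difference of 25 points.

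- Equal q: the difference is 25 × (1 − q), which is 23.75 points at 5%, 22.5 at 10% and 20.0 at 20%.
- q = 9% on drug, 20% on placebo (the planning failure rates): 36.3% − 24.0% = 12.3 points.
- q = 20% on drug, 9% on placebo: 44.0% − 13.55% = 30.45 points.

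The direction is not fixed.

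**5. Effect on the contrast between doses.** Assume p = 0.10 at the lower dose and 0.30 at the higher, a true difference of 20 points. With equal q the difference is 20 × (1 − q). If 25% to 75% of a 9% failure rate received therapeutic anticoagulation (an assumption), q is 2.25% to 6.75%, and the difference becomes 19.55 to 18.65 points, a relative loss of about 2% to 7%. Only unequal contamination would matter: 8.3 points with q = 20% at the lower dose and 9% at the higher, or 25.9 points with these reversed.

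**6. How high must a later value be?** SAP Table 13 puts aPTT Grade 2 above 1.5 × ULN and Grade 3 above 2.5 × ULN. With 35 s as an illustrative ULN (the upper box-plot reference line for Figure 3), these are 52.5 s and 87.5 s. The highest aPTT allowed at entry (42 s) plus the largest mean rise reported from the COPD study (8 s) is 50 s. That is 50/35 = 1.43 × ULN, or Grade 1. With a ULN of 32 s it is 1.56 × ULN, already Grade 2; with 40 s it is 1.25. So, depending on the local ULN, a later value can override a typical on-infusion grade. In Table 16 a later high value changes the maximum cell only where the on-infusion maximum had stayed at or below the ULN.

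**The case against.** The strongest reply has three parts.

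- **The maximum is the protocol's own choice.** Section 9.4.3.2 specifies it, and a whole-study maximum is the inclusive option for safety. This stands as a reason to keep the row. It does not make it the only post-baseline row.
- **Other outputs already help.** Figure 3 shows aPTT by treatment group and visit for scheduled visits only, which is close to an on-infusion display. Table 15 lists aPTT results with date and time, Table 4 gives times for interruptions and discontinuations, and Table 17 dates enoxaparin use. In 24 participants, analysed descriptively, a late value can be found by reading the listings. This is real mitigation. But Figure 3 shows no grades or shifts and includes the early-discontinuation draw, the listings must be joined by hand, and Table 17 does not name unfractionated heparin.
- **The event may be rare.** It needs a draw, its entry, and a value above the on-infusion maximum. Enoxaparin is monitored by anti-Xa. Section 8.3.4 also speaks of entering specified parameters at specified time points, so entry of every later draw is not certain. This stands: the frequency is unknown.

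A reader might go further and infer three things that the documents do not support.

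- **That the dose signal is masked.** With similar contamination in both active arms, the contrast between doses hardly moves (step 5).
- **That on-infusion values are bounded at 50 s, so higher grades must come mainly from later anticoagulation.** Protocol section 7.1 acts after such a value has been recorded, and those values enter the maximum.
- **That contamination must be larger on placebo.** This presumes efficacy in these small cohorts.

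**Conclusion.** The point holds as a missing on-treatment window. A post-drug value under therapeutic anticoagulation can set the only post-baseline grade or shift displayed for a participant, and one such participant is worth 12.5 to 25 percentage points of an arm. The effect on the drug-placebo contrast can go either way: under the assumptions shown, a true 25 points could appear as anything from about 12 to about 30. The contrast between the two doses is little affected unless contamination differs between them. The values of p and q are assumptions, and the planning failure rates are only a proxy for post-drug anticoagulation. The route and the weight of one participant follow from the documents; the frequency does not. The change is worth making because it is nearly costless and concerns a named risk of the drug.

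**What to change.** In Table 14 add, for aPTT and INR, a row with the maximum grade from first dose to last infusion stop plus a short lag stated in the SAP. In Table 16 add the corresponding on-infusion maximum for aPTT, PT, INR and anti-Xa. Read arm comparisons from these rows. Keep the whole-study maximum that protocol section 9.4.3.2 specifies as a second row, labelled as including results after study drug.

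The cost is one date/time filter and one extra row per parameter. Infusion start and stop times are recorded in the eCRF (protocol section 6.5), and laboratory dates and times already feed Table 15. The downside is fewer values per participant in the new row. The row also does not isolate the drug effect: permitted heparin or enoxaparin prophylaxis, and any anticoagulation given while study drug continues, still contribute to it.
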